[figure not shown]
TITLE: Rapid plasma genotyping for early initiation of erlotinib in *EGFR* mutant lung cancer

PROTOCOL NUMBER :	16-093
STUDY DRUG:	Erlotinib
PRINCIPAL INVESTIGATOR :	[name].
CO-INVESTIGATORS :	[name]. Ph.D. [name].
STATISTICIAN:	[name].
SPONSOR:	Dana-Farber Cancer Institute

SCHEMA – DIAGNOSTIC PHASE

**Participants showing clinical benefit to erlotinib may continue to receive study treatment beyond disease progression with the approval of the treating investigator.

SYNOPSIS

Study Title:	Rapid plasma genotyping for early initiation of erlotinib in EGFR mutant lung cancer					
Cán day Dhagaa	II					
Study Phase:						
Study Rationale:	Plasma genotyping using a ddPCR-based platform has been demonstrated to rapidly, accurately and noninvasively detect targetable genomic alterations such as EGFR sensitizing mutations (exon 19 del and L858R) in advanced lung adenocarcinoma. This study will evaluate a new diagnostic and treatment paradigm in which newly diagnosed or progressive advanced lung adenocarcinoma patients will undergo rapid plasma genotyping followed by immediate initiation of erlotinib therapy in patients with detected EGFR mutations.					
Primary Objective(s):	Demonstrate a high objective response rate to erlotinib in patients with advanced NSCLC positive for an EGFR mutation by plasma genotyping.					
Secondary Objective(s):	 Determine the time from study registration to treatment initiation using a rapid plasma genotyping strategy versus standard tumor genotyping. Ascertain the positive predictive value of plasma genotyping for patients with recently diagnosed advanced NSCLC. 					
Study Design:	Open-label single-arm phase II study					
Study Population:	Patients with newly diagnosed, progressive or recurrent advanced lung adenocarcinoma with clinical characteristics that increase the likelihood of possessing an EGFR mutation (never/light smokers or Asian race); all subjects must have tumor biopsy tissue available for analysis at enrollment or a plan to obtain this tissue. Re-biopsy at the development of treatment resistance is encouraged.					
Study Size:	100 patients will be screened in the diagnostic portion of this study using a CLIA plasma genotyping assay. 30 patients positive for an EGFR mutation by this assay will continue in the treatment portion of this trial with immediate treatment with erlotinib.					
Drug, Dose, and Mode of Administration:	Erlotinib 150 mg orally daily.					
Drug Manufacturer:	Astellas					
Duration of Treatment:	Until disease progression or intolerable toxicity					
Efficacy Assessments:	CT assessment of response per RECIST v1.1 will be performed every 6 weeks for a total of 24 weeks.					
Correlative Analysis:	If technically feasible, baseline tumor biopsy material should be available for standard EGFR genotyping.					
Statistical Methods:	available for standard EGFR genotyping.Treatment with erlotinib among those who test positive for an EGFRsensitizing mutation (exon 19 del/L858R) via plasma genotyping will beconsidered worthy of further study if the lower bound of the two-sided90% exact binomial confidence interval around the objective responserate exceeds 0.40; this is consistent with observing at least 17 responses(CR or PR) among the 30 patients enrolled on the study.					

CONFIDENTIAL

Date of Original Approved
Protocol:April 26, 2016Date of Most Recent
Protocol Amendment (if
applicable):February 15, 2017

TABLE OF CONTENTS

Syno	opsis	ii
1.	OBJECTIVES	1
1.	1 Study Design	1
1.	2 Primary Objectives	1
1.	3 Secondary Objectives	1
2.	BACKGROUND	1
2.	1 Study Disease	1
2	2 Plasma Genotyping	2
2	3 Study Assay	2
2	4 Study Agent	4
2	5 Rationale	4
3.	PARTICIPANT SELECTION	4
3.		
3.	2 Exclusion Criteria	5
3	3 Inclusion of Women, Minorities and Other Underrepresented Populations	6
4.	REGISTRATION PROCEDURES	6
4.	.1 General Guidelines for DF/HCC and DF/PCC Institutions	6
4.	.2 Registration Process for DF/HCC and DF/PCC Institutions	6
4.	.3 General Guidelines for Other Participating Institutions	6
4.	4 Registration Process for Other Participating Institutions	6
5.	STUDY PROCEDURES	6
5.	1 Initial Plasma Genotyping	6
5	2 Serial Plasma Genotyping	7
5	3 Tissue Genotyping	7
6.	TREATMENT PLAN	7
6.	1 Pre-treatment Criteria	8
6.	.2 Agent Administration & Storage	8
6.	3 Definition of Dose-Limiting Toxicity	9
6.	4 General Concomitant Medication and Supportive Care Guidelines	9
6.	5 Duration of Therapy	9
6.	6 Treatment Assessments	10
6.	7 Duration of Follow Up	10

CONFIDENTIAL

Protocol: 16-093: Rapid Initiation of Erlotinib for Advanced NSCLC Using Genotyping of Cell-free Plasma DNA

Version	n date: February 15, 2017	
6.8	Criteria for Removal from Study	
7. E	XPECTED TOXICITIES AND DOSING DELAYS/DOSE MODIFICATIONS	11
7.1	Anticipated Toxicities	11
7.2	Toxicity Management	11
7.3	Dose Modifications/Delays	12
8. D	PRUG FORMULATION AND ADMINISTRATION	12
8.1	Erlotinib	12
9. C	CORRELATIVE/SPECIAL STUDIES	13

1. OBJECTIVES

1.1 Study Design

This single-arm phase II study will treat 30 patients with erlotinib based upon a positive plasma genotyping assay revealing an EGFR activating mutation (exon 19 del, L858R). To identify these 30 patients, we will screen 100 patients with newly diagnosed, progressive or recurrent advanced NSCLC that have not yet undergone standard genotyping. This study will examine a novel treatment strategy utilizing rapid plasma genotyping and immediate erlotinib treatment in EGFR mutant patients. The study population will be enriched in never/light smokers and patients of Asian race. All patients will undergo rapid plasma genotyping followed by immediate treatment in EGFR mutant patients. Standard tissue genotyping will be performed in parallel if adequate tumor tissue is available; for those without tissue available for genotyping at study start, a biopsy to confirm tumor genotype and assess resistance is expected at the end of study. Patients where biopsy fails and is not felt to be feasible or safe may still go on treatment if an EGFR mutation is detected by plasma genotyping. Given the high specificity & positive predictive value of this assay, false positive results are rare. Patients will undergo baseline CT imaging which will be repeated initially after 6 weeks and then at 12, 18 and 24 weeks. Patients will continue on erlotinib until they develop clinically significant progression as per current standard of care. Re-biopsy upon the development of treatment resistance will be encouraged but will not be covered by this study. The primary statistical analysis of response rate will be performed in 30 patients initiating erlotinib therapy based on plasma genotype.

1.2 Primary Objectives

- Demonstrate a high objective response rate to erlotinib in patients with advanced NSCLC positive for an *EGFR* mutation (exon 19 del/L858R) by plasma genotyping.

1.3 Secondary Objectives

- Determine the time from study registration to treatment initiation using a rapid plasma genotyping strategy versus standard tumor genotyping.
- Ascertain the positive predictive value and false negative rate of plasma genotyping for patients with recently diagnosed advanced NSCLC among patients with tissue available for standard genotyping.

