Following initial validation of this assay in a small group of patients as described above, we retrospectively examined this assay in a larger group of metastatic NSCLC patients with EGFR sensitizing mutations (exon 19 del, L858R) and acquired resistance to EGFR kinase inhibitors. This study compared the test characteristics of our ddPCR-based plasma genotyping assay for the detection of both EGFR sensitizing and the T790M acquired resistance mutation in a cohort of 41 patients with advanced NSCLC who had undergone re-biopsy and standard tissue genotyping for comparison. This revealed 70% assay sensitivity for detection of EGFR T790M and a 93% assay specificity to T790M. In addition, a subset of 15 of these patients underwent serial plasma genotyping after beginning a new line of systemic/targeted therapy. This subset of patients underwent baseline plasma genotyping followed by repeat testing with each treatment cycle. Patients with a partial response to treatment uniformly exhibited decreased levels of *EGFR* cfDNA over time whereas patients without response exhibited stable or increased levels [Figure 2].¹⁴ These data indicate that this assay may also predict treatment outcome as early as 4 weeks after initiating treatment – potentially allowing early treatment modification.

We have subsequently initiated a prospective study of ddPCR-based plasma genotyping in a planned cohort of 340 NSCLC patients in order to assess its ability to accurately detect *EGFR* sensitizing (exon 19 del, L858R), T790M and *KRAS* G12X mutations. These patients include newly diagnosed patients, those with acquired resistance to kinase inhibitors and those undergoing a new line of subsequent treatment. The aims of this study include assessing both test characteristics compared to gold standard tissue genotyping performed on a biopsy specimen as well as correlating change in detectable levels of mutations

during treatment with radiographic response through serial blood testing. This study has accrued 250 patients thus far. Median TAT for plasma ddPCR is 3 days (range 1-5). Specificity of plasma ddPCR is 99% for 19 del/L858R (94/95) and 100% for *KRAS* (82/82), but lower for T790M at resistance (81%, 22/27). Sensitivity

[figure not shown]

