Figure 2: change in *EGFR* mutation copy number in advanced NSCLC patients with (A) and without (B) a partial radiographic response after initiating a new line of therapy (PR – partial response, SD – stable disease, PD – progressive disease per RECIST 1.1).

[figure not shown]

Figure 3: log-fold change in mutation copy number in advanced NSCLC patients correlates with radiographic response in patients treated with both standard chemotherapy and kinase inhibitors (per RECIST 1.1).

of plasma ddPCR is 75% for 19 del/L858R (73/97) and 73% for T790M (30/41) but lower for *KRAS* (62%, 16/26).

Taken together, these previous studies indicate that ddPCR-based plasma genotyping using our validated assay is able to detect *EGFR* sensitizing mutations (exon 19 del, L858R) in metastatic NSCLC with a

high degree of specificity and acceptable sensitivity. A positive result from this assay is thus highly specific for the presence of an *EGFR* mutation and clinically actionable given the very low likelihood of false positive results.

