3. PARTICIPANT SELECTION

3.1 Eligibility Criteria

Participants must meet the following screening criteria in order to enroll and undergo plasma genotyping on this study:

- 3.1.1 Histologically or cytologically confirmed metastatic NSCLC including recurrent disease
- 3.1.2 *EGFR* genotype must not be known. However, pending *EGFR* tumor genotyping is allowed.
 - 3.1.2.1 Participants with positive or pending EGFR mutation on plasma genotyping performed at the central lab are eligible for enrollment, and will not need to repeat initial plasma genotyping on study.

CONFIDENTIAL

3.1.3 Tissue must be available for genotyping or biopsy planned to obtain tissue for genotyping. Biopsy requirement may be waived if not technically feasible and plasma genotyping reveals an eligible *EGFR* mutation (exon 19 del/L858R). Determination of technical feasibility must be made independently of plasma genotyping results.

- 3.1.4 Participants must possess at least two of the following clinical characteristics which enrich for *EGFR* mutations:
 - smoked less than 10 pack years
 - Asian race
 - Adenocarcinoma (including adenosquamous carcinoma) on histology or cytology.
- 3.1.5 Participants must have measurable disease with at least one lesion that can be accurately measured in longest dimension as >2 cm with conventional imaging techniques or >1 cm with a spiral CT scan per RECIST v1.1.
- 3.1.6 Participants must have progressive, advanced cancer as defined by one of the following:
 - Newly diagnosed, untreated advanced disease
 - Newly diagnosed, untreated metastatic recurrence of earlier stage disease (previous treatment of early stage disease allowed).
 - Clinical determination of progressive disease on previous systemic therapy as evidenced by plan to change treatment. Any number of prior therapies are acceptable excluding previous EGFR kinase inhibitors.
- 3.1.7 Age 18 years or older.
- 3.1.8 ECOG performance status 0-2.
- 3.1.9 Participant must be able to understand and give consent to participate in the study.
- 3.1.10 Patient must be a candidate for systemic therapy with erlotinib based on clinical assessment. Patients must meet the following criteria before beginning therapy (Note: these are not required for initial study enrollment and plasma genotyping):
 - ECOG performance status of 0-2
 - Platelets >75
 - AST & ALT < 3x the upper limit of normal
 - Creatinine clearance > 30 mL/min by Cockroft-Gault
 - No other contraindication to erlotinib

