10. STUDY CALENDAR

Baseline evaluations including a history, physical exam, vitals, relevant blood work, and baseline imaging are to be conducted within 4 weeks prior to start of protocol therapy. Laboratory studies must be drawn within 7 days of starting study drug.

All assessments must be performed prior to administration of any study medication. All study assessments should be administered within \pm 7 calendar days of the protocol-specified date, unless otherwise noted.

Re-imaging of sites of disease should be performed every 6 weeks for 24 weeks after the initiation of study drug, and then at least every 3 months thereafter as per standard of care. Follow-up tumor assessments may be made within \pm 7 calendar days of the protocol-specified date.

Protocol: 16-093: Rapid Initiation of Erlotinib for Advanced NSCLC Using Genotyping of Cell-free Plasma DNA

Version date: February 15, 2017

		ГІС PHASE eatment)				EUTIC PHASE eatment cycles)	
Test/Procedure	Enrollment: (within 4 weeks of start)	Registration ^e	Day 1 Cycle 1 ^f	Day 14 Cycle 1	Day 1 Cycle 2, 3, 4	Every 2-3 months (per institutional standard) after completing Cycle 4	End of Study Within 30 days of off study
Observations						0,000	
Informed	Х						
Consent							
History and Physical Examination	Х		Х	Х	Х	Х	Х
Vital signs, weight	Х		Х	X	X	Х	Х
Height	Х						
ECOG PS	Х		Х	Х	Х	X X	X X
Assessment of high-grade adverse events			Х	X	X	Х	Х
Review of Drug Diary					X	Х	Х
Dispense 6-week supply of erlotinib			Х		X	Х	
Tests & Labs							
Serum chemistry ^a			Xb	X	Х	Х	
CBC with diff			Xb	X	X	X	
Serum or urine pregnancy test			Xg				
Recommend biopsy/re-biopsy & order genotyping if available ^c	Х						Х
Collect 3 10 cc EDTA tubes of blood for plasma genotyping ^d		X					
Collect single 10 cc EDTA tube of blood for plasma genotyping			Х	Х	Х	Х	Х
Imaging		1		T	1		
Chest CT +/- abdomen	Х				X*	Х	Х
Brain MRI or CT	Х						

a: Albumin, alkaline phosphatase, total bilirubin, BUN, calcium, chloride, creatinine, glucose, phosphorus, potassium, total protein, SGOT [AST], SGPT [ALT], sodium, magnesium ^bLaboratory studies must be drawn within 7 days of starting study drug.

Protocol: 16-093: Rapid Initiation of Erlotinib for Advanced NSCLC Using Genotyping of Cell-free Plasma DNA

Version date: February 15, 2017

[°]If biopsy for tumor genotyping is not performed prior to starting therapy, then biopsy to confirm tumor genotype is expected, if technically feasible, after progression on study.

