15.2 Sample Size/Accrual Rate

100 participants recruited over a 2 year period will undergo plasma genotyping for potential treatment with erlotinib on study. It is anticipated that approximately 30 patients will be positive for an EGFR (exon 19 del/L858R) sensitizing mutation by plasma. After recruitment of 50 patients is complete, the accrual rate and number of patients treated with erlotinib will undergo re-assessment for feasibility.

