15.4 Analysis of Secondary Endpoints

From a total of 100 NSCLC patients studied, we estimate that 30 will have an *EGFR* sensitizing mutation (exon 19 del/L858R), respectively, based upon prior prevalence data at our institution. Concordance between tumor and plasma genotyping results will be calculated using a Cohen's kappa. The potential clinical value of the ddPCR genotyping assay will be estimated using:

• Positive predictive value (PPV): To be clinically useful, the PPV must exceed 90% for the plasma assays for *EGFR* and *KRAS* mutations.

• Sensitivity: The sensitivity of each assay must exceed 70% to have clinical value.

• Efficiency: The turnaround time (TAT) between ordering the plasma genotyping and obtaining the result will be compared to the TAT for tumor genotyping. We will compute the turnaround time for each, and compare them using the Wilcoxon-test. To have maximal clinical value, the median TAT for plasma genotyping must be less than 3 days.

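### Sensitivity is computed only in patients with tissue, but only plasma-positives can have tissue waived, so the 70% comparison is open to partial-verification bias in either direction

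*Combined protocol and SAP*

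**What the plan says.** - **Analysis set.** Section 1.3 restricts the positive predictive value and false-negative rate to patients "among patients with tissue available for standard genotyping". Section 15.4 does not repeat the restriction, but sensitivity against tumor genotype cannot be computed without tissue.
- **Bar.** Section 15.4: "The sensitivity of each assay must exceed 70% to have clinical value". It gives no rule for patients without a tissue result.
- **Waiver.** Section 3.1.3 asks for tissue or a planned biopsy from everyone. The biopsy requirement can be waived only if biopsy is infeasible and plasma shows an eligible mutation. Sections 1.1 and 5.3 likewise let plasma-positives be treated when biopsy fails or cannot be done.
- **Safeguards.** Section 3.1.3 adds: "Determination of technical feasibility must be made independently of plasma genotyping results". Footnote c to the Study Calendar (section 10) adds: "If biopsy for tumor genotyping is not performed prior to starting therapy, then biopsy to confirm tumor genotype is expected", if feasible and after progression.
- **Known positives.** Section 3.1.2.1: "Participants with positive or pending EGFR mutation on plasma genotyping performed at the central lab are eligible for enrollment".
- **Plasma-negatives.** Sections 6.1.1 and 6.8 follow them only until standard therapy starts and then remove them. No tissue result is required first.

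**The concern.** Sensitivity in verified patients is unbiased only if, among patients with mutant tumors, the chance of having a tissue result is the same for plasma-positives and plasma-negatives. The design gives reasons for it to differ.

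- A true positive without tissue drops out of both numerator and denominator, which pulls the estimate down.
- A false negative who starts standard therapy untested drops out of the denominator only, which pushes it up.
- A patient enrolled because plasma was already positive adds to both numerator and denominator with no matching chance of a false negative, which also pushes it up.

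What is at stake is a pass/fail statement on clinical value. The documented sensitivity is only about 5 points above the bar, so modest differences in verification can affect which side the estimate falls on. Cohen's kappa, also planned in 15.4, is computed on the same verified patients.

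**Working it through.** **Inputs from the documents.** Section 2.3 gives prior sensitivity for exon 19 del/L858R as 73/97. Section 15.4 sets the bar at 0.70. Section 15.2 states: "It is anticipated that approximately 30 patients will be positive for an EGFR (exon 19 del/L858R) sensitizing mutation by plasma", out of 100 screened. Section 15.4 instead expects 30 of 100 to carry a sensitizing mutation. At 75% sensitivity these are different populations, so counts are shown for both.

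**Inputs assumed.** Let v+ and v- be the fractions of mutant plasma-positives and mutant plasma-negatives with a tissue result. The documents give neither.

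**Step 1. Reproduce the documented figure.** 73/97 = 0.753, matching the stated 75%.

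**Step 2. Verified-only sensitivity.**

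Se_obs = Se·v+ / [Se·v+ + (1 − Se)·v−], with Se = 0.7526 and 1 − Se = 0.2474.

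| v+ | v- | Se_obs |
|---|---|---|
| 0.80 | 0.80 | 0.753 |
| 0.90 | 1.00 | 0.732 |
| 0.90 | 0.95 | 0.742 |
| 0.80 | 0.95 | 0.719 |
| 0.70 | 0.95 | 0.691 |
| 0.60 | 0.95 | 0.658 |
| 0.90 | 0.80 | 0.774 |
| 0.95 | 0.70 | 0.805 |

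For example, at v+ 0.80 and v- 0.95: 0.6021/(0.6021 + 0.2351) = 0.719.

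**Step 3. Break-even.** Setting Se_obs = 0.70 gives v+/v- = (0.70/0.30) × (24/73) = 0.767. With v- = 0.95, this is v+ = 0.73.

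**Step 4. In counts, with every mutant plasma-negative verified.**
- 30 true plasma-positives imply 30 × 24/73 = 9.86 false negatives. Losing 7 positives gives 23/32.86 = 0.6999, just under the bar.
- 30 tissue mutants imply 22.6 true positives and 7.4 false negatives. Losing 5 gives 0.703 and losing 6 gives 0.691.

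**Step 5. Known positives under 3.1.2.1.** Take 30 mutants at 0.753 and add an assumed 5 known true positives. Full-verification sensitivity becomes 27.58/35 = 0.788. With v- = 0.95 and v+ = 0.80, 0.70 or 0.60 it is 0.758, 0.732 or 0.701. With 3 entrants it is 0.744, 0.717 or 0.685. The number of such entrants is not documented.

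**Step 6. Does a Begg-Greenes estimate repair it?**

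Se = P(plasma+)·PPV / [P(plasma+)·PPV + P(plasma−)·(1 − NPV)].

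For illustration, take 100 patients, 30 plasma-positive with PPV 1, and 10 mutants among the 70 plasma-negatives. True sensitivity is 30/40 = 0.75. With v+ 0.80 and v- 0.95, the verified-only figure is 24/(24 + 9.5) = 0.716. PPV and NPV are unchanged if verification depends only on the plasma result, so Begg-Greenes returns 0.30/(0.30 + 0.70 × 10/70) = 0.75. If 5 known positives are counted in P(plasma+), it becomes 35/105 = 0.333 and the estimate rises to 0.333/(0.333 + 0.667 × 10/70) = 0.778. The plasma-positive proportion must therefore exclude them.

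**The case against.** A reader might infer that sensitivity is biased downward, on the argument that plasma-negatives need tissue to choose therapy while plasma-positives do not. The documents do not support that as a firm statement. Section 2.1 presents tissue biopsy as the existing route to genotype, and section 5.3 treats tissue EGFR and ALK testing as standard of care, so the argument is plausible. But no section requires a tissue result before a plasma-negative patient starts therapy, and sections 6.1.1 and 6.8 end their follow-up at that point. Low v- is as possible as low v+, and 3.1.2.1 pushes upward.

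The safeguards also narrow the gap. Everyone needs tissue or a biopsy plan at enrollment. Genotyping of available tissue must already be ordered or pending, often before an on-study plasma result is known. Infeasibility judged independently of plasma affects both groups, and equal fractions give no bias. A later confirmatory biopsy is expected. These points stand, but they do not close the gap. A plan is not a result, and the later biopsy is conditional on feasibility and, under section 5.3, not reimbursed. For 3.1.2.1 entrants with a positive result in hand, the documents describe no means of keeping that result from whoever judges feasibility.

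Finally, the effect is modest against sampling error. With 30 mutants the standard error is √(0.7526 × 0.2474/30) = 0.079. With no bias at all, the point estimate fails to exceed 70% about 31% of the time (21 or fewer detected of 30). A 3-point shift is under half a standard error. This limits the weight of the point, but noise does not excuse an avoidable bias that leans on the same verdict.

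**Conclusion.** The comparison with the 70% bar is open to partial-verification bias, and section 15.4 does nothing about it. Direction and size cannot be settled from the documents, because they give neither the verification fractions nor the number of known-positive entrants. If true sensitivity is 73/97 and no known positives enter, the verified-only estimate falls below 0.70 only when v+/v- is under about 0.77. A 10% relative deficit costs about 2 points (0.732), and a deficit among plasma-negatives raises the estimate. The break-even assumes that the earlier cohort's sensitivity carries over to this trial. The endpoint is secondary and does not enter the response-rate success rule in 15.1, so this is a cheap and worthwhile improvement and does not threaten the trial's main conclusion.

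**What to change.** Amend section 15.4 as follows.

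1. Tabulate tissue verification by plasma result, showing 3.1.2.1 entrants with a known positive separately.
2. Beside the verified-only sensitivity and false-negative rate, report the Begg-Greenes estimate in Step 6 with a bootstrap confidence interval, taking PPV and NPV from verified patients.
3. Take P(plasma+) only from patients whose plasma result was unknown at registration, excluding 3.1.2.1 entrants with a known positive. Otherwise the corrected estimate is itself inflated.
4. State whether tissue obtained after progression counts as the reference.

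The cost is a few lines of SAP text and code, using data the study already collects and leaving patient care unchanged. The downsides are that the correction assumes tissue availability depends on genotype only through the plasma result, and that the interval is slightly wider.
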